By preparing for new and future SARS-CoV-2 variants of concern (i.e., BA.4 and BA.5 currently increasing in prevalence) this protocol is being updated to include a 600 mg dose with an administered frequency of 6 months over 12 months to maintain the efficacy. The 600 mg IM dose selected for this sub-study extension is based on the 600 mg dose administered in the TACKLE study, and 600 mg AZD7442 is authorized for emergency use in the USA since 24 February 2022; both of which demonstrated a generally safe and well-tolerated safety profile.

Group level recruitment caps may be placed to ensure 50 or more participants complete the study with their assigned dose and valid samples. Approximately 150 participants from the USA may be selected from the existing participants enrolled on the sub-study with an approximately even distribution coming from the 2 existing groups to receive repeat doses

of 600 mg IM. This approach will maintain a balanced sample across the 3 groups to support descriptive analysis for PK and safety at each dose schedule. Immunosuppressed participants will be prioritized to be enrolled into the new 600 mg IM dosing study group. This is in line with the indication for which the product is currently authorized for emergency use in the USA.

Specific changes of the sub-study CSP addendum are as follows:

Section 1.1 (Synopsis)

The sub-sections were updated to include the new 600 mg repeat dose participant study arm, extended study duration, and interim analyses. In addition the Cardiovascular Event Adjudication Committee was added to align with other AZD7442 studies.

Section 1.2 (Schematic)

The schematic has been updated to include the additional repeat dose participant arm and extended study duration.

Section 1.3 (Schedule of Activities)

A new Schedule of Activity table has been included for extended sub-study treatment and follow-up periods of the additional repeat dose participant groups. In addition the COVID-19 monitoring schedule for all groups were aligned.

Section 2.3.1 (Risk Assessment)

The table was updated to align with the current Investigator Brochure and SAE occurrence updated

Section 3 (Objectives and Endpoints)

The section has been updated to include the additional repeat dose participant arm.

Section 4.1 (Overall Study Design)

The section has been updated to include the additional repeat dose participant arm and extended study duration.

Section 4.2 (Scientific Rational for the Study Design)

The section has been updated to include the rational for the additional repeat dose participant arm and extended study duration.

Section 4.3 (Justification for Dose)

The section has been updated to include the justification of the 600 mg dose.

Section 6 (Study Intervention)

This section was edited to update status of the AZD7442 products.

Section 6.1 (IMPs Administered)

The section has been updated to include the additional repeat dose participant dose, extended study duration, and the new IMP dose used.

Section 6.2 (Preparation/Handling/Storage/Accountability)

The section has been updated to include new dose used.

Section 6.3 (Measure to Minimize Bias: Randomization and Blinding)

The section has been updated to include new dose used.

Section 6.5 (Concomitant Therapy)

Table 10 (Permitted, Restricted and Prohibited Medications) updated to align with other AZD7442 studies.

Section 8.1 (Efficacy Assessments)

The Section 8.1.1 (Monitoring COVID-19 Symptoms) has been updated to include the additional repeat dose participant arm schedule of activities for monitoring COVID-19 symptoms. In addition, language in Section 8.1.3 (Illness Visits) was added for clarification.

Section 8.4 (Overdose)

The section has been updated to include new dose used.

Section 8.5.2 (Immunogenicity Assessments)

Section 8.5.2.5 (Additional Serum Immunogenicity) updated to reflect what is in SoA. In addition serological assessments moved into Section 8.5.3 Pharmacodynamics.

Section 9.1 (Statistical Hypothesis)

The section has been updated to include new dose used.

Section 9.2 (Sample Size Determination)

Paragraph added to justify participant numbers chosen for the groups within this amendment.

9.4.2 (Secondary Endpoints)

Paragraph added to account for new COVID-19 treatments available.

Section 9.7 (Adjudication Committees)

This section was split into 2 sub-sections (Morbidity Adjudication Committee and newly added Cardiovascular Event Adjudication Committee) for 2 committees to align with other AZD7442 studies.

A5

Details on DSMB structure were

Various sections

Clarifications have been made where appropriate as well as other minor editorial and document formatting revisions **throughout**.

TABLE OF CONTENTS

TITLE P	'AGE	1
PROTO	COL AMENDMENT SUMMARY OF CHANGES TABLE	2
TABLE	OF CONTENTS	6
1	PROTOCOL ADDENDUM SUMMARY	10
1.1	Synopsis	10
1.2	Schematic	
1.3	Schedule of Activities	13
2	INTRODUCTION	31
2.1	Study Rationale	31
2.2	Background	31

1 PROTOCOL ADDENDUM SUMMARY

1.1 Synopsis

Sub-study Title: A Phase III, Multi-center, Open-label Sub-study in Adults to Assess the Safety, Pharmacokinetics (PK), and Immunogenicity of Repeat Doses of AZD7442, a Combination Product of Two Monoclonal Antibodies (AZD8895 and AZD1061) (The PROVENT Repeat Dose Sub-study).

Rationale: AZD7442 is being evaluated for the prevention and treatment of Coronavirus Disease 2019 (COVID-19). PROVENT is an ongoing Phase III randomized, double-blind, placebo-controlled, multi-center study in adults to assess the safety and efficacy of a single dose of AZD7442 for pre-exposure prophylaxis of COVID-19 (PROVENT parent study). This PROVENT sub-study will assess the safety, PK, and immunogenicity of repeat doses of AZD7442 in participants currently enrolled in the PROVENT study who may benefit from a repeat dose of AZD7442. This sub-study will investigate whether additional doses of AZD7442 have an appropriate safety profile in this vulnerable population. Pharmacokinetic data will also be generated to evaluate whether repeat dosing can maintain serum concentrations of AZD7442 levels associated with protection against COVID-19.

Objectives and Endpoints:

Table 1 presents the objectives and endpoints for the repeat dose sub-study.

Table 1 Objectives and Endpoints for the Repeat Dose Sub-Study

Objective	Endpoint
Primary	
To evaluate the safety and tolerability of repeat doses of AZD7442 300 and 600 mg IM	AEs, SAEs, MAAEs, and AESIs post repeat dose of IMP
Secondary	
To evaluate the PK of repeat doses of AZD7442 300 and 600 mg IM	Serum AZD7442 concentrations after repeat dosing PK parameters if data permit after repeat dosing
To evaluate ADA responses to repeat doses of AZD7442 300 and 600 mg IM in serum	Incidence of ADA to repeat doses of AZD7442 in serum
To determine anti-SARS-CoV-2 nAb levels in serum following repeat doses of AZD7442 300 and 600 mg IM	Post dose GMTs and GMFRs from baseline values after a repeat IM dose in SARS-CoV-2 nAbs (wild-type assay or pseudo-neutralization assay)

ADA, antidrug antibody; AE, adverse event; AESI, adverse event of special interest; GMT, geometric mean titer; GMFR, geometric mean fold rise; IM, intramuscular; IMP, investigational medicinal product; MAAE, medically attended adverse event; nAb, neutralizing antibody; PK, pharmacokinetic; SAE, serious adverse event; SARS-CoV-2, severe acute respiratory syndrome-coronavirus 2.

For Exploratory objectives, see Section 3.

Overall Design:

This is a Phase III, multi-country, multi-center, open-label, sub-study assessing the safety, PK, and immunogenicity (ADA) of repeat doses of AZD7442. Participants at a subset of active PROVENT parent study sites in participating countries will be invited to enroll in this sub-study.

Participants will be adults who have been randomized and are actively participating in the PROVENT parent study and who may benefit from a repeat dose of AZD7442. There is no screening period in the sub-study and participants will retain their subject identification number from the parent study.

Participants will be eligible for inclusion in the sub-study once they have reached 12 ± 2 months post dose of IMP in the double-blind parent study. Eligible participants who have already completed their Day 366 Visit in the parent study will be unblinded, assigned to a sub-study group, and then undergo the sub-study Day 1 (SS-D1) assessments. For participants who have not yet completed their Day 366 Visit in the parent study, the SS-D1 visit will include the Day 366 assessments. Pre-dose Day 366 assessments will serve as baseline assessments for the sub-study.

All participants will receive AZD7442 in the repeat dose sub-study. Initially, participants will be assigned to one of two dosing interval groups, based on their double-blind IMP assignment in the parent study, as follows:

- Group 1 (~ 12-month repeat dose interval): Participants who received AZD7442 300 mg IM on Day 1 of the parent study will receive a second dose of AZD7442 300 mg IM on SS-D1.
- Group 2 (~ 6-month repeat dose interval): Participants who received placebo on Day 1 of the parent study will receive their first dose of AZD7442 300 mg IM on SS-D1 followed by a second dose on SS-D183.

At 6 months (SS-D183), a subset of participants from USA sites in Group 1 and Group 2 (evenly balanced between groups), who consent to receive additional AZD7442 600 mg doses approximately every 6 months will be assigned to a new arm - Group 3. All other participants will continue in the sub-study according to their originally assigned dosing interval group schedule. The addition of Group 3 will create 4 possible dosing cohorts, based on the how many doses of 300 mg AZD7442 received prior to entering Group 3 and whether or not this was followed by a further two doses of 600 mg AZD7442:

Group 1

Cohort 1: AZD7442 300 mg, 300 mg

Group 2

Cohort 2: Placebo, AZD7442 300 mg, 300 mg

Group 3

- Cohort 3 (from Group 1): AZD7442 300 mg, 30 0mg, 600 mg, 600 mg
- Cohort 4 (From Group 2): Placebo, AZD7442 300 mg, 600 mg, 600 mg

Group level recruitment caps may be placed to ensure 50 or more participants complete the study with their assigned dose and valid samples.

Group 1 and Group 2 will undergo safety follow-up for 456 days after the last dose of AZD7442, and Group 3 will undergo safety follow-up for 183 days after the last dose of AZD7442 (Figure 1).

Disclosure Statement: This is a safety/PK/immunogenicity study with three arms (all AZD7442 but with different doses, dosing intervals and/or study durations) that is not blinded.

Number of Participants: Approximately 500 participants will be enrolled from the parent PROVENT study into the sub-study and receive AZD7442. The aim is to approximately balance the proportion of participants derived from each of the AZD7442 and placebo arms from the double-blind parent study. If an imbalance between the arms is observed, a cap may be introduced.

To investigate repeat dosing with 600 mg IM, participants in the USA sites will be offered the option to be enrolled to receive repeat doses of 600 mg in Group 3 from SS-D183 onwards.

Intervention Groups and Duration: All participants will receive a repeat dose of AZD7442. The planned duration of the sub-study is 457 days for Group 1, 639 days for Group 2, and 548 days for Group 3.

Data Safety Monitoring Board: The independent DSMB monitoring the PROVENT parent study will provide safety oversight, to ensure safe and ethical conduct of the sub-study.

Statistical Methods

Primary Endpoint: The safety and tolerability of AZD7442 will primarily be assessed by the incidence of AEs, SAEs, MAAEs, and AESIs.

Interim analysis: An initial interim analysis is planned after a minimum of 50 participants at the first stage of enrollment of Group 1, who received AZD7442 on Day 1 of the parent PROVENT study have received a repeat dose of AZD7442 on SS-D1 and followed until SS-D29 (ie, for 28 days after their second dose of AZD7442). This interim analysis will assess the primary safety endpoint and available secondary endpoints. The first Data Review Meeting by

[figure not shown]
the DSMB will occur in conjunction with the interim analysis. Additional interim analyses may be conducted as required for any future regulatory commitments.

Morbidity Adjudication Committee: An independent Morbidity Adjudication Committee will assess blinded data to evaluate whether the causes of death for participants are considered COVID-19 associated.

Cardiovascular Event Adjudication Committee: An independent Cardiovascular Event Adjudication Committee will provide an independent, external, systematic, and unbiased assessment of de-identified blinded data to systematically evaluate cardiovascular events.

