8.1.1 Monitoring COVID-19 Symptoms

To determine the incidence of infection, study sites will contact participants weekly (telephone/email/text) through to the SS-D183 and then monthly to the end of the study, with reminders to monitor for COVID-19 symptoms and cardiac events. During these contacts the Investigator will enquire about any COVID-19 symptoms (see Table 11) and cardiac events from the past 7 days or month respectively and will need to initiate Illness Visits within 3 days if such symptoms are reported. Participants who present with at least one of the COVID-19 qualifying symptoms listed in Table 11, must contact the study site.

Participants who present with a COVID-19 qualifying symptom(s) after SS-D1 will be instructed to initiate Illness Visits and will be tested locally for SARS-CoV-2 (see Section 8.6.1.1). If negative at Illness Visit D1, the participant will be instructed to stop Illness Visits and continue with the with the sub-study scheduled assessments (ie, Table 2, Table 3, or Table 4). If positive, the participant will be instructed to continue to complete all Illness Visits and will have additional assessments per Table 5. COVID-19 qualifying symptom(s), SARS-CoV-2 positive test results, and/or COVID-19 diagnosis will be collected and recorded in the eCRF as an AE.

Table 11 COVID-19 Qualifying Symptoms

Participant must present with at least one of the following symptoms:		
Duration	Symptom	
No minimum duration	Fever	
	Shortness of breath	
	Difficulty breathing	
	New onset confusion (only for participants ≥ 60 yo)	
	Appetite loss or decrease food intake (only for participants ≥ 60 yo)	
	Increased supplemental oxygen requirement (only for participants ≥ 60 yo on baseline supplemental oxygen)	
Must be present for ≥ 2 days	Chills	
	Cough	
	Fatigue	
	Muscle aches	
	Body aches	
	Headache	
	New loss of taste	
	New loss of smell	
	Sore throat	
	Congestion	
	Runny nose	
	Nausea	
	Vomiting	
	Diarrhea	

Adapted from CDC 2021

CDC, Centers for Disease Control and Prevention; yo, years old.

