8.3.5 Medically Attended Adverse Events

Medically attended adverse events will be collected according to the time points specified in the SoA (see Section 1.3).

Medically attended adverse events are defined as AEs leading to medically attended visits that were not routine visits for physical examination or vaccination, such as an emergency room visit, or an otherwise unscheduled visit to or from medical personnel (medical doctor) for any reason. Adverse events, including abnormal vital signs, identified on a routine study visit or during the scheduled Illness Visits will not be considered MAAEs.

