8.3.6 Adverse Events Based on Signs and Symptoms

All AEs spontaneously reported by the participant or care provider, or reported in response to the open question from the study site staff: 'Have you had any health problems since the previous visit/you were last asked?', or revealed by observation, will be collected and recorded in the eCRF. When collecting AEs, the recording of diagnoses is preferred (when possible) to recording a list of signs and symptoms. However, if a diagnosis is known and there are other signs or symptoms that are not generally part of the diagnosis, the diagnosis and each sign or symptom will be recorded separately. Symptoms of COVID-19, confirmed SARS-CoV-2 infection, and/or diagnosis of COVID-19 will be collected and recorded in the eCRF as an AE.

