8.3.7 Adverse Events Based on Examinations and Tests

The results from the protocol-mandated laboratory tests, vital signs, ECG, and other safety assessments will be summarized in the CSR.

Deterioration, as compared to baseline in protocol-mandated safety assessments, should therefore only be reported as AEs if they fulfill any of the SAE criteria, are the reason for discontinuation of treatment with the IMP, or are considered to be clinically relevant as judged by the Investigator (which may include, but not limited to, consideration as to whether treatment or non-planned visits were required or other action was taken with the IMP, eg, dose adjustment or drug interruption).

If deterioration in a laboratory value/vital sign is associated with clinical signs and symptoms, the sign or symptom will be reported as an AE and the associated laboratory result/vital sign will be considered as additional information. Wherever possible, the reporting Investigator uses the clinical, rather than the laboratory term (eg, anemia versus low hemoglobin value). In the absence of clinical signs or symptoms, clinically relevant deteriorations in non-mandated parameters should be reported as AE(s).

Any new or aggravated clinically relevant abnormal medical finding at a physical examination, as compared with the baseline assessment, will be reported as an AE, unless unequivocally related to the disease under study.

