9.4.1 Safety: Primary Endpoint

9.4.1.1 Primary Endpoint(s)

The safety of AZD7442 will primarily be assessed by:

- Incidence of AEs
- Incidence of SAEs
- Incidence of MAAEs
- Incidence of AESIs

The AE severity will be graded according to Appendix B and coded using the most recent version of the Medical Dictionary for Regulatory Activities. Adverse events will be presented for each dosing interval group by system organ class and preferred term. Summaries will include the number and percentage of participants reporting at least one event, number of events, and exposure adjusted rates, where appropriate.

An overview of AEs will be presented for each group, including the number and percentage of participants with any AE and SAEs. Summaries will present the relationship to IMP as assessed by the Investigator, maximum intensity, seriousness, and death.

A listing will cover details for each individual AE.

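### COVID-19 events count in the primary any-AE and SAE incidences, and no summary without them is specified

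*Protocol*

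**What the plan says.** The protocol synopsis states the primary endpoint: "The safety and tolerability of AZD7442 will primarily be assessed by the incidence of AEs, SAEs, MAAEs, and AESIs". Section 9.1 adds that nothing is tested, so these incidences are themselves the primary result.

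Two sections bring COVID-19 into the AE data. Section 8.1.1: "COVID-19 qualifying symptom(s), SARS-CoV-2 positive test results, and/or COVID-19 diagnosis will be collected and recorded in the eCRF as an AE". Section 8.3.6: "Symptoms of COVID-19, confirmed SARS-CoV-2 infection, and/or diagnosis of COVID-19 will be collected and recorded in the eCRF as an AE".

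Section 9.4.1.1 then sets the summaries. The overview reads: "An overview of AEs will be presented for each group, including the number and percentage of participants with any AE and SAEs". The breakdown reads: "Adverse events will be presented for each dosing interval group by system organ class and preferred term". It also plans summaries by relationship to IMP, intensity, seriousness and death, a listing of each AE, and exposure-adjusted rates where appropriate. None of these leaves COVID-19 events out.

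Some rules do limit the overlap:

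- Section 8.3.6 on recording: "When collecting AEs, the recording of diagnoses is preferred (when possible) to recording a list of signs and symptoms".
- Section 8.3.5 on MAAEs: "Adverse events, including abnormal vital signs, identified on a routine study visit or during the scheduled Illness Visits will not be considered MAAEs".
- The AESI list in Section 8.3.4 does not contain COVID-19.
- Section 9.7.1 has deaths adjudicated for association with COVID-19.

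The SAP supplied covers the single-dose parent study. It splits deaths by COVID-19 relationship (Section 18.2), but its AE summaries (Section 18.1) also include none without COVID-19.

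**The concern.** A safety incidence that contains the prevented disease moves with community infection and with protection, as well as with tolerability. In a randomised, concurrent comparison the infection pressure would be shared. Here it need not be:

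- Nobody is randomised to 600 mg. Group 3 consists of consenting participants at USA sites (Section 4.1), and the amendment summary says that immunosuppressed participants are prioritised.
- Repeat-dose time starts at SS-D1 in Group 1 and at SS-D183 in Group 2. The 600 mg doses also start at SS-D183.
- Safety follow-up after the last dose is 456 days in Groups 1 and 2 and 183 days in Group 3.
- Symptom contact is weekly to SS-D183 and monthly afterwards (Section 8.1.1). Group 1's first six repeat-dose months are therefore queried weekly, while Group 2's repeat-dose time and all 600 mg time are queried monthly.

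A group followed through a larger wave could look less well tolerated, and a more protective regimen could look safer. Section 4.2 also asks whether safety after a repeat dose is comparable to safety after a single dose. That comparison is open to the same shift.

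**Working it through.** **The plan's own figure.** Section 9.2 gives a probability above 99% of seeing at least one AE in 500 participants at a true rate of 1%. The check is 1 − 0.99^500 = 0.9934, so it reproduces. It does not depend on which terms are counted, and nothing below changes it.

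**Which components are affected.**

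| Component | COVID-19 content |
|---|---|
| Any AE | Symptoms, positive tests and diagnoses all count |
| SAE | A COVID-19 hospitalisation counts (Appendix B 2) |
| MAAE | Events found at scheduled Illness Visits are out; an emergency visit for COVID-19 is in |
| AESI | Essentially none |

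**Whether the planned tables separate it.** A recorded COVID-19 diagnosis has its own preferred term row. A symptom recorded without a diagnosis is coded to its own term. Headache, nausea and fever are qualifying symptoms in Table 11. Headache and nausea are also mild post-injection reactions in Table 15, and fever with rigors appears there under severe reactions, so a row for such a term can mix reactogenicity with infection. Appendix B 3 classes deterioration from lack of effect as not related, which places it among all other unrelated events. The any-AE and SAE overview is not split at all.

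**Observation windows on the sub-study-day scale.** Group 1 runs SS-D1 to SS-D457 (456 days) and Group 2 from its repeat dose runs SS-D183 to SS-D639 (456 days). They share 457 − 183 = 274 days. Group 3 from the first 600 mg dose runs SS-D183 to SS-D548 (365 days), wholly inside Group 2's window.

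**Size, illustration only.** The documents give no AE or COVID-19 rate for the sub-study. Let q be the non-COVID AE incidence and c the proportion with a COVID-19 AE, assumed independent. Then any-AE incidence = 1 − (1 − q)(1 − c), and COVID-19 adds (1 − q)c.

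1. *Contribution.* For q from 30% to 70% and c from 5% to 30%, it runs from 0.3 × 0.05 = 1.5 points to 0.7 × 0.30 = 21 points.
2. *Different attack rates.* With 10% against 25%, the gap is (1 − q) × 0.15.
   - q = 30%: 0.7 × 0.15 = 10.5 points
   - q = 40%: 46% against 55%, 9 points
   - q = 60%: 0.4 × 0.15 = 6 points
3. *Different follow-up only.* Take c = 1 − exp(−rate × days/365.25), q = 50%, and 456 against 365 days.
   - 0.05 per year: c = 0.061 and 0.049, gap 0.5 × 0.012 = 0.6 points
   - 0.40 per year: c = 0.393 and 0.329, gap 0.5 × 0.064 = 3.2 points
4. *Different protection only.* Take q = 50%, 1.25 years, and the infection rate halved in one group.
   - 0.1 per year: 55.9% against 53.0%, 2.9 points
   - 0.4 per year: 69.7% against 61.1%, 8.6 points

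**The case against.** The strongest reply is that AEs count events whatever their cause, and that COVID-19 belongs in the safety data because Table 6 lists antibody-dependent enhancement as a potential risk. This stands, and it is why the all-AE tables must stay. It is no argument against a second set.

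Next, no formal decision rests on crude any-AE incidence. There is no hypothesis, and the suspension triggers in Section 7.4 concern IMP-related findings, hypersensitivity and injection site reactions. This also stands. The issue is interpretation, not a wrong figure.

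A separate COVID-19 analysis may also exist. The exploratory rows of Table 7 are redacted, and its footnote defines COVID-19 and RT-PCR although neither appears in the visible rows. Section 8.5.2.2 measures infection by seroconversion as well. A hidden case count would show infection by group, but would not by itself take those events out of the AE tables.

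The calendar argument is limited too. Groups 1 and 2 overlap for 274 of 456 days and Group 3 lies inside Group 2's window, so timing matters mainly between Group 1 and the others. Planned exposure-adjusted rates would reduce the follow-up effect in item 3, but not differences in attack rate or protection.

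A reader might infer four stronger points that the documents do not support:

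- *That COVID-19 is nowhere distinguished.* The preferred term tables, relationship summaries, MAAE rule and death adjudication each do so in part. Section 8.3.6 prefers the diagnosis and asks for separate recording only of symptoms not generally part of it, so leakage is partial.
- *That participants are dosed without a test result.* Section 5.1 requires a negative RT-PCR within 3 days or a negative rapid antigen test. The central swab is an additional baseline sample.
- *That Section 8.3.7 contradicts this rule.* Its exception ("will be reported as an AE, unless unequivocally related to the disease under study") concerns physical-examination findings only.
- *That 25/5150 is the parent study's attack rate.* The primary analysis was triggered at about 24 events or 30% unblinding (SAP Section 4.4), pools a 2:1 allocation, and censors at unblinding or receipt of a preventive product. The denominator is planned enrolment.

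**Conclusion.** The point holds in a limited form. COVID-19 events enter the any-AE and SAE incidences fully and the MAAE incidence partly, while AESIs are essentially untouched. Section 9.4.1.1, which is not redacted, specifies no summary that excludes them, and the separations that do exist are incomplete. Crude incidences across non-randomised groups can therefore differ with no difference in tolerability.

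The size cannot be fixed from the documents. The 6 to 10.5 points rest on assumed attack rates of 10% and 25%, an assumed non-COVID AE incidence of 60% down to 30%, independence, and every infection producing a recorded AE. With equal infection risk the distortion would largely vanish. No sub-study SAP was available, so table choices made there cannot be judged. This is a worthwhile improvement to a descriptive primary result, not an error in the design or in a stated figure.

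**What to change.** In Section 9.4.1.1, define a derived flag for AEs belonging to an RT-PCR-confirmed SARS-CoV-2 episode: the diagnosis, the positive test, and qualifying symptoms dated within the episode. The Illness Visit episode labels in Section 8.1.3 offer a basis for the dates. Then present, by cohort:

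- AE, SAE and MAAE incidence and exposure-adjusted rates excluding flagged events;
- the all-AE tables, unchanged, alongside;
- COVID-19 events in a table of their own, if the redacted exploratory analyses do not already provide one.

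Collection and expedited reporting stay as they are. The cost is one derivation and a second set of tables from data already collected. One limit should be stated with the tables: infections never confirmed by RT-PCR stay in the non-COVID summaries, and less frequent contact may leave more of them unconfirmed.
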